11. TREATMENT DISCONTINUATION/PATIENT WITHDRAWAL

Patients may withdraw from the study at any time and for any reason. Study drug administration may also be discontinued at any time, at the discretion of the investigator. In any case, follow-up for efficacy and safety should be continued in subjects that discontinue therapy, but remain in the study (i.e., ODIS patients).

11.1. Reasons for Early Study Drug Discontinuation

Study drug discontinuation should be avoided as much as possible, but may be done for any of the following reasons:

- Patient withdraws consent or requests early discontinuation from the study for any reason. Patients should be encouraged to continue to participate in the study for the entire duration of the study even if they choose not to take study medication any longer.
- Occurrence of a clinical or laboratory AE, either serious or non-serious, at the discretion of the investigator. The Sponsor or designee should be notified if a patient discontinues study drug because of an AE or laboratory abnormality. It is recommended that, unless clear contraindications arise, patients be strongly encouraged to adhere to their treatment regimen with the study drug for the duration of the trial. Any interruptions of therapy should, if possible, be brief (e.g., <4 weeks) and only for clinically indicated reasons, such as AEs. The following should be considered reasons for study drug discontinuation:
 - ALT >3 × ULN and bilirubin > 1.5 × ULN
 - ALT >5 × ULN
 - ALT >3 × ULN and appearance or worsening of hepatitis
 - ALT >3 × ULN persisting for >4 weeks
 - ALT >3 × ULN and cannot be monitored weekly for 4 weeks
- Any medical condition or personal circumstance that, in the opinion of the investigator, exposes the patient to risk by continuing in the study or precludes adherence to the protocol.
- Sponsor discontinues the study.
- Investigative site closure, in the event that:
 - Another investigative site cannot accommodate the patient, or
 - The patient is unable or unwilling to travel to another investigative site.
- A TG value that is flagged as critically high, i.e., >1000 mg/dL (11.29 mmol/L), and confirmed as critically high by a repeat measurement (new fasting blood sample) within 7 days. In this case, a patient may be discontinued from study drug (with the option to remain ODIS) and other lipid-altering medications may be (re)initiated. If the TG value is flagged as >2000 mg/dL (22.58 mmol/L) then appropriate medical action can be taken by the investigator as soon as possible.

Occurrence of an outcome event according to the judgment of the investigator is not considered a valid reason for study drug discontinuation.

Patients whose treatment with study medication is discontinued early, and have not withdrawn consent, will stay in study and will be monitored until the end of the study. Patients who continue in the study after ≥ 30 days after cessation of therapy will be characterized as ODIS. ODIS patients should be asked to return to the study site for an interim visit once the patient has been off study drug for >30 days. Procedures at this visit are consistent with those at Visit 5. If not contraindicated, patients will also have the option to restart study medication at any point once characterized as ODIS. For patients who discontinue study medication (e.g., for an AE that may or may not be drug-related), a brief therapy interruption can be followed with a re-challenge (re-initiating study medication) as soon as clinically appropriate; thereby allowing a causative role for study medication to be confirmed or ruled out and continuing a patient in the study and on study drug if appropriate.

The reason for study drug discontinuation or interruption will be recorded on the CRF.

11.2. Follow-Up after Early Study Drug Discontinuation/Lost to Follow-Up

- Patients who prematurely discontinue study drug are not to be replaced.
- All randomized patients must be followed up according to the study schedule of procedures until the study end date or death, regardless of whether they discontinue study drug prematurely or not. Any event occurring after early study drug discontinuation will be recorded up through the study end date.
- In order to follow the medical status of the patients, especially when they discontinued the study, investigators are encouraged to obtain information from the patient's primary care practitioner (physician or any other medical care provider). Investigators are also requested to try as much as possible to re-contact those patients at the end of the trial to obtain at least their vital status as well as their status with respect to the primary endpoint, and thus avoid lost to follow-up for the efficacy assessment.
- If patients are lost to follow-up, the CRF must be completed up to the last visit or contact.

12. STATISTICS

12.1. Analysis Populations

12.1.1. Intent-to-Treat Population

The Intent-to-Treat (ITT) population will include all patients who are randomized via the IWRS. All efficacy analyses, including the primary analysis, will be performed on the ITT population. Patients will be analyzed according to the randomized treatment.

12.1.2. Modified Intent-to-Treat Population

The Modified Intent-to-Treat (mITT) population will include all randomized patients who have study drug dispensed after randomization. Groups will be defined based on the randomized treatment.

12.1.3. Per-Protocol Population

The Per-Protocol (PP) population will include all mITT patients without any major protocol deviations, and who had $\geq 80\%$ compliance while on treatment. To be included in the PP population the minimum time on therapy is 90 days.

12.1.4. Safety Population

All safety analyses will be conducted based on the Safety population, which is defined as all randomized patients. This is the same as the ITT population.

12.2. Statistical Methods

Safety and efficacy variables will be analyzed using appropriate statistical methods to be described in detail in a separate Statistical Analysis Plan (SAP). The SAP will be finalized before study unblinding.

12.2.1. Patient Disposition and Demographic/Baseline Characteristics

The number and percentage of patients will be tabulated for each of the following categories for each treatment group:

- Screened (total only);
- Re-screened and reasons for re-screening (total only);
- ITT overall and by stratification factors (CV risk, ezetimibe use, and geographical region);
- mITT population; overall and by stratification factors (CV risk, ezetimibe use, and geographical region);
- PP population; overall and by stratification factors (CV risk, ezetimibe use, and geographical region);
- Safety population;
- Patients who complete the study;
- Patients who terminated from the trial early and the primary reason for early termination.
- Patients who terminated the trial early; prior to having a confirmed primary endpoint event.

- Patients with complete follow-up, defined as those for whom all components of the primary endpoint have been ascertained during the entire observation period (or until death).
- Patients who, at the time of study completion, were discontinued from study drug prematurely, but continued within the study (i.e. ODIS patients), along with the primary reason.

For randomized patients who discontinued treatment with study drug, the primary reason for discontinuation will be listed and summarized by treatment group.

Demographic and baseline characteristics, including age, gender, ethnicity, race, height, body weight, BMI, diabetes, hypertension, metabolic syndrome, overweight/obese/normal according to BMI, and diabetes plus obesity will be summarized using descriptive statistics by treatment group in the ITT population.

Demographic data and baseline characteristics will be also compared between treatment groups for the mITT population and PP population. Differences in demographic and baseline characteristics will be tested using a chi-square test (for categorical variables) or t-test (for continuous variables). The p-values will be considered descriptive, primarily as an assessment of the balance between groups. Age in years will be calculated using the date of randomization (Visit 2) and the date of birth.

12.2.2. Study Medication Exposure and Compliance

Study drug exposure will be summarized by treatment group using descriptive statistics for each time point and overall. Overall study drug compliance will be calculated as the number of doses assumed to be taken relative to scheduled dosing period as follows:

$$\text{Compliance (\%)} = \frac{(\# \text{ Capsules of total dispensed} - \# \text{ Capsules of total returned})}{(\text{last dose date} - \text{first dose date} + 1) \times 4 \text{ capsules/day}} \times 100$$

Overall percent compliance will be calculated per patient in the ITT and Modified ITT populations and summarized by treatment group using descriptive statistics.

12.2.3. Concomitant Therapies

Concomitant medication/therapy verbatim terms will be coded using the latest available version, prior to data base lock, of the World Health Organization Drug Dictionary and the Anatomical Therapeutic Chemical classification system. The numbers and percentages of patients in each treatment group taking concomitant medications will be summarized. All verbatim descriptions and coded terms will be listed for all non-study medications.

12.2.4. Analysis of Efficacy

For efficacy endpoints including CV events, only adjudicated events will be included in the final statistical analyses.

12.2.4.1. Summary Statistics

Summary statistics (n, mean, standard deviation, median, minimum, and maximum) for the baseline and post-baseline measurements, the percent changes, or changes from baseline will be presented by treatment group and by visit for all efficacy variables to be analyzed. The

summary statistics will include changes in body weight and BMI from baseline by treatment group and by visit.

12.2.4.2. Primary Endpoint Analyses

The primary endpoint is described in [Section 9.2.1](#). The analysis of the primary endpoint will be performed using the log-rank test comparing the 2 treatment groups (AMR101 and placebo) and including the stratification factor “CV risk category”, use of ezetimibe and geographical region (Westernized, Eastern European, and Asia Pacific countries) (each as recorded in the IWRS at the time of enrollment) as covariates. The two-sided alpha level for the primary analysis will be reduced from 0.05 to account for the interim analyses based on a group sequential design with O’Brien-Fleming boundaries generated using the Lan-DeMets alpha-spending function. The hazard ratio for treatment group (AMR101 vs. placebo) from a Cox proportional hazard model that includes the stratification factor will also be reported, along with the associated 95% confidence interval. Kaplan-Meier estimates from randomization to the time to the primary endpoint will be plotted.

The size and direction of the treatment effects of the individual components of the composite endpoint and their relative contribution to the composite endpoint will be determined as well.

All observed data that are positively adjudicated by the CEC, including data after discontinuation of study treatment for patients who discontinue study drug prematurely, will be included in the primary analysis.

Patients who do not experience a primary efficacy event prior to the end of the study or who withdraw from the study early without a preceding primary efficacy event will be censored at the date of their last visit/phone contact.

The longest prespecified interval between visits (onsite or phone) is 90 days. In view of the up to 90-day monitoring period for CV events, the primary endpoint for patients who have a non-CV death within 90 days of last contact without having had an earlier CV event will be censored at the time of death. The primary endpoint for patients who have a non-CV death more than 90 days after last contact without having had an earlier CV event will be censored at the time of last contact.

The primary analysis will assume that all silent MIs occurred on the date of the first tracing indicative of a silent MI; a second (sensitivity) analysis will assume that all silent MIs occurred on the day after the last prior normal ECG; and a third (sensitivity) analysis will assume that all silent MIs occurred at the mid-point between the last normal ECG and the ECG with the new MI.

All deaths causally adjudicated as “undetermined” will be combined with those adjudicated as “CV deaths” for the primary analysis. A sensitivity analysis of the CV death category will be performed that excludes the “undetermined cause of death” cohort.

The primary efficacy analysis will be performed on the ITT population. A sensitivity analysis will be performed using the mITT and PP populations.

As a sensitivity analysis, patients who discontinue study drug prematurely will be censored for the primary composite endpoint analysis on the date of drug discontinuation. The primary analysis will be repeated using this censoring rule for the mITT population.

As a supportive analysis, a multivariable, stratified Cox proportional hazards model will be constructed for the primary endpoint to evaluate the treatment effect adjusting for important covariates.

12.2.4.3. Secondary Endpoint Analyses

The key and other secondary endpoints are listed in [Section 9.2.2](#). The key secondary hypothesis will be tested as part of the confirmatory process only if the primary analysis is statistically significant. For the analysis of secondary efficacy endpoints, the Type 1 error will be controlled by testing each endpoint sequentially, starting with the key endpoint. Testing will be done at a significance level consistent with that used for the primary endpoint and will cease when a secondary endpoint is found for which treatments do not significantly differ. P-values will be presented for all analyses, but they will be considered descriptive after the first non-significant result is obtained.

Each of the secondary endpoints will be analyzed by the same methods described for the primary efficacy endpoint. Kaplan-Meier estimates, the log-rank test stratified by stratification factors used at randomization, and the Cox proportional hazards model including the stratification factors as specified above for the primary efficacy endpoint, will be summarized by treatment group. In view of the 90-day monitoring period for CV events, the key secondary endpoint for patients who have a non-CV death within 90 days of last contact without having had an earlier CV event will be censored at the time of death. The key secondary endpoint for patients who have a non-CV death more than 90 days after last contact without having had an earlier CV event will be censored at the time of last contact. Kaplan-Meier curves stratified by each stratification factor will be presented. These analyses will be conducted for the ITT population.

12.2.4.4. Tertiary Endpoint Analyses

The tertiary endpoints are listed in [Section 9.2.3](#). Time-to-event tertiary endpoints will be analyzed by the same methods as described for the primary efficacy endpoint. Kaplan-Meier estimates, the log-rank test stratified by stratification factors used at randomization, and the Cox proportional hazards model as specified for the primary efficacy endpoint, will be summarized by treatment group. In view of the 90-day monitoring period for CV events, if applicable, tertiary endpoints for patients who have a non-CV death within 90 days of last contact without having had an earlier CV event will be censored at the time of death. If applicable, tertiary endpoints for patients who have a non-CV death more than 90 days after last contact without having had an earlier CV event will be censored at the time of last contact. Kaplan-Meier curves stratified by each of the stratification factors will be presented.

The fasting lipid panel is tested at Screening (Visit 1 or Visit 1.1), Randomization visit (Visit 2; Day 0), Visit 3 (Day 120; ~4 Months) and all other follow-up visits including the last visit. For change from baseline to 1 year preparative ultracentrifugation measurements for LDL-C will be analysed, unless this value is missing. If the LDL-C preparative ultracentrifugation values are missing, then another LDL-C value will be used, with prioritization of values obtained from LDL-C Direct measurements, followed by LDL-C derived by the Friedewald calculation (only for subjects with TG <400 mg/dL), and finally LDL-C derived using the calculation published by Hopkins University investigators (Martin 2013). In addition, change from baseline to day 120 in LDL-C utilizing Friedewald's and Hopkins methods will be analysed, using the arithmetic mean of LDL-C obtained at Visit 2

(Day 0) and the preceding Visit 1 (or Visit 1.1). If one of these values is missing, the single available LDL-C value will be used. LDL-C according to Hopkins will be calculated at each visit.

The randomization visit will be considered Baseline. If a baseline value is not available from the randomization visit, then the latest screening value will be used.

For measurements of lipids, lipoproteins, and inflammatory markers, the change from baseline and the percent change will be summarized at each visit. Since these parameters are typically not normally distributed, the Wilcoxon rank-sum test will be used for treatment comparisons of the percent change from baseline, and medians and quartiles will be provided for each treatment group. The medians of the differences between the treatment groups and 95% CIs will be estimated with the Hodges-Lehman method. In addition, shift –tables may be generated as appropriate.

As an additional exploratory analysis, the relationship between post-baseline biomarker values and treatment effects with the primary and key secondary endpoints will be assessed by adding biomarker values (for example, at 4 month, or at 1 year, etc.) as time-dependent covariates in the Cox proportional hazards model. Diagnostic plots for the proportional hazards assumption will be evaluated

Weight is measured at the screening visit and at all follow-up visits, including the last visit of the study. Waist circumference will be measured at the randomization visit (Visit 2; Day 0), Visit 5 (Day 720) and the last visit of the study. Descriptive statistics will be presented by visit and treatment group for baseline, post-treatment change from baseline, and the percent change from baseline. Analysis methods for repeated measurements will be used to compare percent change from baseline between treatments.

New onset diabetes is defined as Type 2 diabetes newly diagnosed during the treatment/follow-up period (i.e. patients with no history of diabetes at randomization, with the test as listed in [Appendix C](#)).

12.2.4.5. Exploratory Subgroup Analyses

Analyses of the effects that patients off study drug and withdrawn from study have on the primary endpoint will be performed.

Subgroup analyses of the primary and key secondary endpoints will be performed as described for the primary endpoint. For each subgroup, Kaplan-Meier estimates, the log-rank test stratified by stratification factors used at randomization (except where the subgroup is a stratification factor), and HRs and CIs from the Cox proportional hazards model as specified for the primary efficacy endpoint, will be summarized by treatment group.

The following subgroups will be explored:

Demographics:

- gender;
- age at baseline (<65 years and ≥65 years);
- race (white and nonwhite, or any other subset with at least 10% of the total number of patients);
- geographical region (Westernized, Eastern European, and Asia Pacific countries); and

- baseline ezetimibe use (yes/no).

Disease Parameters:

- CV risk category;
- the presence/absence of diabetes at baseline; and
- renal dysfunction at baseline (estimated glomerular filtration rate [eGFR] <60 mL/min/1.73m²) using the Chronic Kidney Disease Epidemiology Collaboration (CKD-EPI) equation as follows:

$$eGFR = 141 \times \min(S_{cr}/\kappa, 1)^\alpha \times \max(S_{cr}/\kappa, 1)^{-1.209} \times 0.993^{Age} \times 1.018 \text{ [if female]} \times 1.159 \text{ [if black]}$$

Where:

S_{cr} is serum creatinine in mg/dL,

κ is 0.7 for females and 0.9 for males,

α is -0.329 for females and -0.411 for males,

min indicates the minimum of S_{cr}/κ or 1, and

max indicates the maximum of S_{cr}/κ or 1 (Levey 2009).

Treatment Parameters:

- statin intensity at baseline (statin type and regimen)
Statin intensity categories as defined in ACC/AHA Cholesterol Guidelines (Stone 2013) and patient's 10-year CV Risk Score (Goff 2013).

Baseline Lipid and Lipoprotein Parameters:

- LDL-C (by tertile);
- HDL-C (by tertile, and tertile by gender);
- TG (by tertile, and tertile by gender);
- RLP-C (by tertile)
- TG ≥150 mg/dL and TG <150 mg/dL;
- TG ≥200 mg/dL and TG <200 mg/dL;
- TG ≥ median, TG < median;
- combined highest tertile for TG and lowest tertile for HDL-C;
- gender-specific highest tertile for TG and lowest tertile for HDL-C;
- TG ≥ 200 mg/dL with HDL-C ≤35 mg/dL;
- hs-CRP (≤3 mg/L and >3 mg/L) and by gender;
- hs-CRP (≤2 mg/L and >2 mg/L) and by gender;
- Apo B (by tertile); and
- non-HDL-C (by tertile).

A Cox proportional hazard (PH) model as mentioned above but additionally with baseline TG as a covariate will be fitted to the data at each interim. Diagnostic plots for the PH assumption will be evaluated.

The consistency of the treatment effects in subgroups will be assessed for the primary and key secondary efficacy endpoints. For each subgroup variable, a Cox PH model with terms for treatment, stratification factors (with the exception of those subgroup variables related to the stratification factors, i.e., CV risk category), subgroup, and treatment-by-subgroup interaction will be performed. The main treatment effect will not be tested with this model. P-values for testing the interaction terms < 0.15 will be considered significant. Results will be presented in a Forest plot.

All subgroup analyses will be conducted for the ITT, mITT and PP populations.

12.2.4.6. Interim Efficacy Analyses

Two interim analyses are planned for the primary efficacy endpoint using adjudicated events when approximately 60% (967 events) and approximately 80% (1290 events) of the total number of primary endpoint events planned (1612) is reached. The planned interim analyses are based on a group-sequential design and are described in the Interim Statistical Analysis Plan (included as an appendix to the SAP) which will be finalized prior to performing the unblinded interim analyses.

The interim results of the study will be monitored by an independent Data Monitoring Committee (DMC). The analyses will be performed by the independent statistical team who is unblinded to the treatment assignment and reported only to the DMC. Unblinded information will not be released to the Sponsor before the completion of the study unless extraordinary circumstances arise and, under such circumstances, procedures for maintaining confidentiality will be described in a written agreement with the DMC. If the study is terminated early following interim analysis, patients will be notified promptly and brought in for their final close-out visit, and the final analyses of efficacy and safety will include all data through their final visit.

All suspected events will be adjudicated in a blinded manner by the CEC.

The time to event will be calculated as the time from randomization to the onset date of the event (as determined by the CEC). Patients who do not experience any of the above events at the time of data cutoff for the interim but are still in the trial will be considered censored at the time of their last regular contact before the interim data cutoff.

12.2.5. Analysis of Safety

All analyses of safety will be conducted on the safety population, which is defined as all randomized patients. The safety assessment will be based on the frequency of AEs, physical exams, vital signs and safety laboratory tests.

AEs with new onset during the study between the initiation of study drug and 30 days after the completion or withdrawal from study will be considered treatment-emergent (TEAEs). This will include any AE with onset prior to initiation of study drug and increased severity after the treatment initiation.

Treatment-emergent adverse events will be summarized by system organ class and preferred term, and by treatment. This will include overall incidence rates (regardless of severity and

relationship to study drug), and incidence rates for moderate or severe AEs. A summary of SAEs and AEs leading to early study drug discontinuation (for ≥ 30 days) will be presented through data listings. Patients who restart study drug will not be included in the summary of AEs leading to discontinuation.

Safety laboratory tests and vital signs will be summarized by post-treatment change from baseline for each of the parameters using descriptive statistics by treatment group. Those patients with significant laboratory abnormalities will be identified in data listings. Additional safety parameters will be summarized in data listings.

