4.2.4 Safety Population

All safety analyses will be conducted based on the Safety population, which is defined as all randomized patients. This is the same as the ITT population.

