4.8.1 Adverse Events

AEs are recorded from the time the informed consent is signed until study participation is complete. Adverse events with onset on or after the date of dispensing study drug for each patient will be considered treatment-emergent (TEAEs). This will include any AE with onset prior to initiation of study drug and increased severity after the treatment initiation.

By design of this study, serious AEs (SAEs) that are endpoint events will only be recorded for the endpoint determination and not captured as SAEs. Following adjudication, if the event is determined to not meet the criteria for an event, the event will be evaluated as an SAE.

Adverse events will be coded using the most recent available Medical Dictionary for Regulatory Activities (MedDRA) Version. Coding includes system organ class (SOC) and preferred term (PT). All AEs will be listed by patient and by SOC and PT; these listings will present detailed information concerning adverse events, including the verbatim description, time of onset and resolution, severity, relationship to study drug, action taken, and outcome.

Pre-treatment AEs:

Pre-treatment-emergent AEs will be defined as any AE that started before the patient's randomization. (An AE that was ongoing at the time of randomization and subsequently increased in severity is also considered treatment-emergent.) Pre-treatment AEs will be listed separately from TEAEs.

Treatment-emergent AEs:

For each patient, the following AEs will be defined as TEAEs:

- AEs occurring after randomization;
- AEs occurring within 30 days after the completion or withdrawal from study;
- AEs started prior to randomization but worsened in severity following randomization;
- AEs with partial onset dates if the AE stop date is after randomization and the dates do not definitively place the AE start date before randomization; and
- AEs with completely missing onset dates.

The frequency and percentage of patients with any TEAEs will be summarized. TEAEs will be presented by SOC and PT. At each summary level, a patient will be counted only once for each TEAE he/she experiences within that level, regardless of how many occurrences of that TEAE that patient experienced. The percentage of patients having had at least one TEAE at each level will be calculated.

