4. OTHER SENSITIVITY, SUPPORTIVE AND EXPLORATORY ANALYSES FOR THE PRIMARY EFFICACY ENDPOINT

This section relates to Section 4.7.1.2 of version 1 of the SAP dated 08 July 2016.

Time-to-event analyses as done for the primary analysis will be carried out at 1-year and 2-year landmarks for the intent-to-treat (ITT) Population. For each landmark, the log-rank test, stratified by stratification variables at randomization (cardiovascular [CV] risk category, use of ezetimibe, and geographical region [Westernized, Eastern European, and Asia Pacific countries]), will be used to compare the time-to-event between treatment groups. Similarly, hazard ratios and 95% confidence intervals will be determined using Cox proportional hazards modelling. Patients without events prior to the landmark time will be censored.

For the recurrent CV events analyses based on 5-component Major Adverse Cardiovascular Events (MACE) (CV death, non-fatal myocardial infarction [MI], non-fatal stroke, unstable angina requiring hospitalization, or coronary revascularization), in addition to the Anderson and Gill and the Li and Lagakos methods specified in the SAP dated 08 July 2016, the total CV event counts will be analyzed using a Negative Binomial Model ([Rogers 2012](#), [Rogers 2014](#), and [Claggett 2018](#)). It will be implemented using SAS Proc Genmod with a log link function, log exposure time as offset, and treatment group and randomization strata as factors.

As additional sensitivity analysis for the primary composite endpoint will be carried out, namely, an on-treatment analysis which includes primary event onset up to 0 and 30-days after permanent discontinuation of study drug.

All SAP Addendum efficacy analyses are considered exploratory and are not included in the formal SAP testing scheme.

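### Adverse events count as treatment-emergent until 30 days after leaving the study, and no AE table restricted to time on drug accompanies them

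*Combined protocol and SAP*

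**What the plan says.** Protocol Section 12.2.5 sets the treatment-emergent window as "AEs with new onset during the study between the initiation of study drug and 30 days after the completion or withdrawal from study". SAP Section 4.8.1 lists "AEs occurring within 30 days after the completion or withdrawal from study" among its treatment-emergent categories. Neither ties the end of the window to the last dose.

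Patients who stop drug are kept in follow-up. Protocol Section 11.1 states: "Patients who continue in the study after ≥ 30 days after cessation of therapy will be characterized as ODIS". Section 11.2 adds: "All randomized patients must be followed up according to the study schedule of procedures until the study end date or death". Section 11 makes clear that this follow-up covers safety as well as efficacy, and Section 10.3.1 extends SAE reporting for these patients to 28 days after study completion. The safety population is every randomized patient; SAP Section 4.2.4 notes: "This is the same as the ITT population".

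SAP Section 4.8.1 tabulates counts and percentages of patients, each counted once per term, without adjustment for time on drug. The only analysis described as on-treatment is in SAP Addendum Section 4, and it concerns efficacy: "an on-treatment analysis which includes primary event onset up to 0 and 30-days after permanent discontinuation of study drug". Addendum Section 8 adds only further coding levels to the AE tables. The optional safety list in Section 4 of the Pre-Specified List of Additional Analyses adds no window linked to last dose.

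Two items come close. SAP Section 4.8.1 tabulates related events and related SAEs separately. Addendum Section 9 limits the liver-injury plots to the treatment period, but does not define that term. Protocol Section 3.3 names only a screening period and a combined treatment/follow-up period, so the phrase need not mean time on drug.

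**The concern.** An event that begins years after the last capsule is labelled treatment-emergent and sits in the same row as events on drug. If the drug raises a risk only while it is taken, off-drug time adds background events to both arms and pulls the ratio between them towards 1. Patients off drug may also, for compelling medical reasons, take lipid-altering medicines otherwise prohibited (Protocol Section 7.2.1), and events on those medicines enter the same tables.

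At stake is whether a reader of the study report can find AE incidence during exposure, above all for the bleeding and hepatic events of special interest in SAP Section 4.8.3. The sponsor judged that off-drug time warranted a sensitivity analysis for efficacy. For safety, where dilution makes the arms look more alike, there is no counterpart.

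**Working it through.** The plan states no figure for this point, so there is none to reproduce. What follows sizes the effect under stated assumptions.

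**Length of follow-up.** Protocol Section 12.3 gives recruitment of 20, 40, 20 and 19% in years 1 to 4 and 1% in the last 0.2 years, with study end at 6.5 years. With uniform entry within each interval, mean potential follow-up is 0.20×6.0 + 0.40×5.0 + 0.20×4.0 + 0.19×3.0 + 0.01×2.4 = 4.6 years (range 2.3 to 6.5). As a check, the same entry pattern with the plan's hazard of 0.053 and hazard ratio of 0.85 gives 1601 expected primary events from 7990 patients, close to the planned 1612. Off-drug time can therefore last years.

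**Relative against absolute effect.** Let L be the background rate, T the follow-up, p the share of follow-up on drug (equal in both arms) and R the on-drug rate ratio, with no effect off drug.
- All follow-up: ratio = pR + (1−p); excess = LT[pR + (1−p)] − LT = LTp(R−1).
- On drug only: ratio = R; excess = LTpR − LTp = LTp(R−1).

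The ratio falls and the excess number of cases does not.

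**Patient-level version, matching the planned tables.** Assumptions, none taken from the documents: background AE hazard λ = 0.01 per year; on-drug hazard ratio h = 1.5; permanent discontinuation hazard d = 0.05, 0.10 or 0.15 per year in both arms; effect gone 30 days after stopping. About 3995 patients per arm is from Protocol Section 3.6. Let A be the fraction AE-free and on drug or within 30 days of stopping, B the fraction AE-free and beyond that, and G(t) the share of patients with potential follow-up longer than t. Then dA/dt = −(λh + d)A, with d acting from day 30, and dB/dt = dA − λB. Incidence is ∫(λhA + λB)G dt for the study-exit window and ∫λhA·G dt for the window ending 30 days after last dose; h = 1 in the placebo arm. Power is for a two-sided 5% comparison of two proportions. Ratios and differences use unrounded values.

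| d per year | Follow-up >30 days off drug | Study-exit window: AMR101 vs placebo, risk ratio | Last dose + 30 days: AMR101 vs placebo, risk ratio | Risk difference (points), exit vs last dose | Power, exit vs last dose |
|---|---|---|---|---|---|
| 0.05 | 10.8% | 6.42 vs 4.48%, 1.43 | 5.94 vs 4.01%, 1.48 | 1.93 vs 1.93 | 96.7 vs 97.8% |
| 0.10 | 20.0% | 6.22 vs 4.48%, 1.39 | 5.34 vs 3.60%, 1.48 | 1.73 vs 1.74 | 93.1 vs 96.5% |
| 0.15 | 27.8% | 6.05 vs 4.48%, 1.35 | 4.82 vs 3.25%, 1.48 | 1.56 vs 1.57 | 87.9 vs 94.7% |

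For h = 1.25 the risk ratio is 1.22 to 1.18 against 1.24, and power 51.5 to 37.1% against 55.5 to 47.1%. If 15% is read as a yearly probability (hazard −ln 0.85 = 0.163), the last row becomes a risk ratio of 1.34 with power 86% against 94%.

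**The case against.** The study-exit window is a defensible choice. It keeps the randomized comparison intact and captures harms that appear late. On-drug rates lose that protection, because patients stop selectively. This stands, and it is why the all-follow-up tables should remain the main display.

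The absolute excess survives under either window, and the planned tables show counts and percentages, where that excess is visible. SAP Section 4.8 plans no formal safety comparisons, so power here only indexes how readily a difference would be noticed. The nearest use of a test is the p-values for flagging at the interim analyses (Interim SAP Section 4.1). This also stands and limits the point to relative measures.

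The plan has partial filters. Relatedness is judged partly on the time course from study drug administration (Protocol Section 10.2), so the related-event tables should remove most events arising years after the last capsule. That is an investigator's judgement, not a window, and does not yield incidence during exposure. The liver plots would be a genuine exception if treatment period means time on drug.

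A reader might infer that patients who tolerated the drug poorly are the most affected. The documents do not support this: the event that caused stopping began on drug, is counted under either window, and also appears among events leading to permanent discontinuation (SAP Section 4.8.1). Only later first onsets of other terms are diluted.

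**Conclusion.** The gap is real and worth closing. What is missing is the companion analysis; the study-exit window itself is sound. No AE, SAE or bleeding table describes time on drug, while the efficacy endpoint has such an analysis.

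The consequence is modest: under the assumptions above, a hazard ratio of 1.5 shows as a risk ratio of 1.43 to 1.35 instead of 1.48, with a loss of about 1 to 7 points of power. This rests on an effect that ends 30 days after stopping, equal discontinuation in both arms and constant rates. The true size cannot be known from the documents, since the sample size makes no allowance for dropout and no discontinuation rate is given.

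A reader might infer that a large share of the harm disappears, for example 40% of the excess if only 60% of follow-up were on drug. That does not follow. The ratio would shrink by that proportion of its distance from 1, but the excess cases are the same under both windows, and nothing in the documents supports so low a share on drug.

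**What to change.** Keep the all-follow-up tables as the main display. Add to SAP Sections 4.8.1 and 4.8.3 a supplementary on-treatment set: treatment-emergent events by system organ class and preferred term, SAEs, bleeding events and hepatic events. Include onsets from first dose to 30 days after permanent discontinuation, the longer of the two Addendum Section 4 windows, and report incidence per 100 patient-years of exposure.

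Give the two sets distinct labels. If the term treatment-emergent is to be reserved for one of them, amend Protocol Section 12.2.5 as well as the SAP. Define treatment period in Addendum Section 9. In the same edit, settle the start of the window: it is drug initiation in Protocol Section 12.2.5, but SAP Section 4.8.1 gives both "Adverse events with onset on or after the date of dispensing study drug for each patient" and onset after randomization.

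Exclude off-drug interruptions only if their start and stop dates are collected. The compliance formula (SAP Section 4.6.7) uses first and last dose dates only, and Protocol Section 11.1 asks only for the reason for an interruption.

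The cost is wording and a second run of existing tables. The date of permanent discontinuation is already needed for SAP Sections 4.6.8 and 4.7.1.2 and Addendum Section 4. The downside is selective stopping, so the added set should be described as supportive only.
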